4.6 Soft tissue thickness

At visit 2 (start of surgery) soft tissue thickness should be measured. For the Osia System, the skin thickness should not exceed 6 mm to ensure optimal retention and

system performance. The measurement should be performed in the center of the marked coil position. For complete instruction, see the surgery guide ⁵.

4.7 Surgery

The surgery is performed at visit 2. After considering all relevant circumstances, factors and information in each case, the appropriate surgical procedure is determined by the responsible investigator exercising independent medical judgment. Complete information is found in the surgery guide ⁵.

During surgery, the following variables should be collected:

- Surgery time (time between first incision and last suture).
- Bone polishing/removal at the actuator site (yes/no).
- BI300 Implant length (3 mm/4 mm).
- Location of BI300 Implant (mm from the ear channel).
- Type of anesthesia (general/local/conscious sedation).
- Soft tissue reduction (yes/no).
- Surgical incision type (C-shaped flap is anterior based for an anterior actuator position or posterior based flap is considered for a more posterior actuator position or other incision type).

At visit 3, approximately 2 weeks after surgery sutures should be removed.

4.8 Intraoperative Test system (IOTS)

At visit 2, in the end of the surgery procedure, the IOTS test should be performed. The test takes approximately two minutes to perform, and the software provides the user with an unambiguous test result regarding device integrity prior to closing and suturing the surgical site. It is crucial that the staff during surgery follow the instruction for use ¹⁰. The software used for the IOTS is installed on a laptop provided by the Sponsor. The software collects data from the transducer of the implant and will assist understanding of the behavior and performance of the transducer once implanted on a recipient. IOTS data will be saved on the laptop until study is ended when it will be transferred to the Sponsor in a coded way.

4.9 Sound Processor fitting

The Osia Fitting Software ⁷ will be used to adjust the investigational device sound processor settings for a specific subject. This will happen during visit 4 when tests will be performed. The fitting software will be installed on a laptop provided by the Sponsor, and the fitting-data will be saved on the laptop until study is ended when it will be transferred to the Sponsor in a coded way.

4.10 Magnet choice

At visit 4 (sound processor fitting) the most suitable magnet should be selected for the sound processor to be tested, and the instruction for use ⁵ should be followed. It is important that the strength is not too weak or too strong. There are 7 different strengths, ranging from ½ to 6. During the following visits, the choice of sound processor magnet should be checked. There may be a need to decrease or increase the strength depending on subject preference.

5 ASSESSMENTS

Assessments, including ancillary measures that will be performed during the clinical investigation are shown in the flow chart, under **Study Test Schedule**.

During the assessments with the study device, the signal processing of the sound processors will be harmonized according to given instructions given in the CRF. This will also be included in the staff training at each participating center during the site initiations.

5.1 Postoperative Audiometric Assessment

Bone conduction thresholds for the study ear will be monitored, to characterize observed unaided thresholds postoperatively. Appropriate masking should be used, if needed, according to local practice. Recognizing that a pediatric subject may not be able to complete measures at all frequencies, minimally thresholds at 500, 1000, 2000, and 4000Hz need to be captured for the study ear.

5.2 Speech, Spatial, and Qualities of Hearing Scale (SSQ-12 version)

The short form of Speech, Spatial, and Qualities of Hearing questionnaire (SSQ-12) from MRC Institute of Hearing Research, UK, is a scaled-down version of the 49 items SSQ questionnaire. It is designed to compile a sub-set of items from the longer original 49 version to represent the scale as a whole, measuring self-reported auditory disability, reflecting the reality of hearing in the everyday world. It has been shown to provide similar results to the standard SSQ ¹². It covers:

- Hearing speech in a variety of competing contexts.
- The directional, distance and movement components of spatial hearing.
- Segregation of sounds and attending to simultaneous speech streams.
- Ease of listening.
- The naturalness, clarity, and identifiability of different speakers, different musical pieces and instruments, and different everyday sounds.

The subjects will complete the SSQ-12 questionnaire at visits 1, 6, and 7.

- At visit 1, the subjects shall complete the SSQ-12 questionnaire prior to testing and shall be answered with respect to an unaided hearing situation, even for subjects with a previous hearing device.
- At visits 6 and 7, the subjects shall complete the questionnaire for the aided situation (with the investigational device).

In the event the subject cannot self-report on the SSQ-12, the SSQ for Parents will be deployed.

5.3 Daily use

During the clinical investigation, data regarding daily use of the sound processor will be collected.

- Average hours of daily use (hours/day) during the last month before visits 5-7.
- SoftWear Pad use (Yes/No) and frequency of change. The number of times the subject changed the SoftWear Pad between study visits.

5.4 Ancillary Assessments

The following measures are ancillary, dependent on the child's capability to complete the tests. If captured, measures will take place in the unaided condition preoperatively, at visit 1, and in the aided condition, using the Osia system, postoperatively.

5.4.1 Free-field thresholds

The purpose of this assessment is to establish hearing thresholds in the free-field through a speaker in the front position (0° azimuth) according to the so-called ascending or modified Hughson-Westlake method (Figure 8). The test shall be performed with the non-test ear blocked (in the case of normal or near-normal hearing, or a large asymmetry with the non-test ear having significantly better hearing thresholds). The signal to be used should be narrow-band noise. Recognizing that a pediatric subject may not be able to complete measures at all frequencies, minimally thresholds at 500, 1000, 2000, and 4000Hz need to be captured.

[figure not shown]

Figure 8: Free-field front speaker position.

5.4.2 Speech recognition in quiet

The purpose of this assessment is to establish the test subject's monosyllabic word recognition in quiet. The test shall be performed at 60 dB SPL using words presented in the free-field through a speaker located in front of the listener, at 0° azimuth (Figure 8). Scores shall be recorded as the percentage of words correctly identified. The test shall be performed with the non-test ear blocked (in cases of normal or near-normal hearing or a large asymmetry with the non-test ear having significantly better hearing thresholds).

6 ADVERSE EVENT AND DEVICE DEFICIENCIES

6.1 Device deficiency reporting

The definition of a device deficiency is “an inadequacy of a medical device with respect to its identity, quality, durability, reliability, safety, or performance.”

Any a device deficiency observed will be fully investigated by the investigator and documented in the case report form (CRF).

A device deficiency that could have led to a Serious Adverse Event (SAE) should be reported immediately (see next section).

6.2 Adverse Events (AE)

6.2.1 Definitions

Term	Definition
Adverse Event (AE)	
Any untoward medical occurrence, unintended disease or injury, or untoward clinical signs (including abnormal laboratory findings) in subjects, users or other persons, whether or not related to the medical device used in the investigation.
 
NOTE 1: This definition includes events related to the investigational medical device or the comparator.
 
NOTE 2: This definition includes events related to the procedures involved.

Adverse Event of Special Interest (AESI)	
An AESI is an AE of scientific and medical concern specific to the Sponsor's product(s).
 
The reporting requirements from the investigator to the Sponsor for an AESI will be the same as the reporting requirements for an SAE.

Adverse Device Effect (ADE)	Adverse event related to the use of an investigational medical device.
Serious Adverse Event (SAE)	
Adverse event that:
 
 a. Led to death. b. Led to serious deterioration in the health of the subject, that either resulted in. c. A life-threatening illness or injury. d. A permanent impairment of a body structure or a body function. e. Led to unplanned in-patient or prolonged hospitalization. f. Medical or surgical intervention to prevent life-threatening illness or injury or permanent impairment to a body structure or a body function. g. Led to fetal distress, fetal death or a congenital abnormality or birth defect. 
NOTE: Planned hospitalization for a pre-existing condition, or a procedure required by the CIP, without serious deterioration in health, is not considered a serious adverse event.

Serious Adverse Device Effect (SADE)	Adverse device effect that has resulted in any of the consequences characteristic of a serious adverse event.
Unanticipated Serious Adverse Device Effect (USADE)	Serious adverse device effect, which by its nature, incidence, severity, or outcome has not been identified in the current version of the risk analysis report.

6.2.2 Adverse Events

An Adverse Event is the development of an untoward medical occurrence or the deterioration of a pre-existing medical condition following or during exposure to an investigational product, whether or not considered causally related to the product or the surgical procedure to implant it. An untoward medical condition can be symptoms (e.g., nausea), signs (e.g., tachycardia, fever) or clinically significant abnormal results of an investigation (e.g., laboratory findings, chest x-ray).

Adverse events that occur during this study may be associated with the implant procedure, including adverse effects from general anesthesia, or specifically associated with the use of the device. An adverse event will be considered to be device-related when, in the judgment of the Primary Investigator, there is a logical connection between the use of the device and the occurrence of the event, above and beyond the study procedure itself.

6.2.3 Adverse Events of Special Interest (Osia Clinical Study only)

The following AEs are defined as adverse events of special interest (AESIs) and should be reported as soon as possible:

- AE that interferes with the daily use of the medical device(s).
- AE at the site of the implant that lead to:
 - Revision surgery including explantation.
 - Severe soft tissue complication.
 - Prescription of antibiotics.

6.2.4 Clinically significant threshold shifts

Shifts in threshold, relative to the preoperative baseline, will be reported as an adverse event (AE) when a shift at any frequency exceeds 15 dB HL.

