To compare the self-reported assessments of hearing outcome with the Investigational device and in a preoperative hearing situation.	
 • Speech, Spatial and Qualities of Hearing Scale -12 (SSQ-12) using the investigational device at 6 months postoperatively vs. the unaided condition preoperatively. • For children unable to complete the SSQ-12: Speech Spatial Questionnaire for Parents using the investigational device at 6 months postoperatively vs. the unaided condition preoperatively.

ANCILLARY OBJECTIVES AND MEASURES

Ancillary measures are additional measures that will be captured only if the child is capable of completing or performing the evaluation as determined by the Investigator.

Ancillary objective	Outcome measures

To compare unaided hearing performance to aided hearing performance using the investigational device.
	
Audiometric: Free-field thresholds (PTA4; mean of 0.5, 1, 2, and 4 kHz) using the investigational device at 6 months postoperatively vs. the unaided condition preoperatively.
 
Speech Perception: Aided monosyllabic words in quiet (% correctly perceived words at 60 dB SPL) using the investigational device at 6 months postoperatively vs. the unaided condition preoperatively.

STUDY TEST SCHEDULE

Visit	1 Preop	2 Surgery	3 Post-op Follow Up	4 Fitting	5	6	7
Visit time point		0	2W	4W	3M	6M	12M
Visit window			± 5D	± 1W	± 2W	± 3W	± 4W
Demographics	X						
Medical history	X						
Baseline characteristics	X						
Eligibility criteria	X						
Informed consent	X						
Soft tissue thickness		X					
Surgery		X					
IOTS		X					
Post-op follow up			X				
Sound processor fitting				X			
Magnet choice				X	X	X	X
Audiogram	X			X ²	X ²	X ²	X ²
Free-field thresholds ¹	X			X	X	X	X
Speech recognition ¹	X			X	X	X	X
Patient reported outcomes	X					X	X
Daily use					X	X	X
Device deficiency		X	X	X	X	X	X
Adverse events		X	X	X	X	X	X
Concomitant medication or treatment		X	X	X	X	X	X
Extra visits	As needed						

¹ These measures are ancillary, dependent on the child's capability to complete the tests. If captured, measures will take place in the unaided condition preoperatively and in the aided condition, using the investigational system, postoperatively.
 
² Bone conduction only.
							

Table of Contents

Synopsis.....	4
Objectives and Outcome Measures.....	6
Study Test Schedule.....	8
1 Introduction.....	14
1.1 Background.....	14
1.1.1 The Baha Systems.....	14
1.1.2 The Osia System.....	14

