3.2 Objectives and outcome measures

Primary objective	Outcome measure
To quantify the type and severity of adverse events in the pediatric population implanted with the Osia system.	Information will be collected from visit 2 through visit 7 of the trial.

Secondary objectives	Outcome measures
To collect surgical information.	
 • Soft tissue thickness • Soft tissue reduction performed • Type of anesthesia • Surgery time • Bone polishing/removal at the actuator site • BI300 Implant length • Location of BI300 Implant • Surgical incision type/location
To collect information about daily use of sound processor (dependent on child's ability to report).	
 • Daily usage time • SoftWear Pad use • Choice of magnet strength
To compare the self-reported assessments of hearing outcome with the investigational device and in a preoperative hearing situation.	
 • Speech, Spatial and Qualities of Hearing Scale -12 (SSQ-12) using the investigational device at 6 months postoperatively vs. the unaided condition preoperatively. • For children unable to complete the SSQ-12: Speech Spatial Questionnaire for Parents using the investigational device at 6 months postoperatively vs. the unaided condition preoperatively.

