4.5 Preoperative Audiometric Assessments

Preoperative unaided audiometric threshold measures (including both air and bone conduction thresholds) should demonstrate that the subject has a conductive, mixed hearing loss or single-sided sensorineural deafness and meets the audiological inclusion criteria.

An existing audiogram is acceptable, as long as it has been completed during the last 6 months, and contains all the required frequencies (minimally air and bone conduction at 500, 1000, 2000, and 4000 Hz) per protocol. The subject's pre-operative PTA4 (pure-tone average of 500, 1000, 2000, and 4000 Hz) should be computed and recorded to ensure the subject meets the inclusion criteria.

If an audiogram is older than 6 months and/or does not contain required frequencies, an entirely new audiogram should be performed at visit 1. Contralateral masking should be used, if needed, according to local practice. The hearing care professional shall always record the unmasked threshold and record the masked threshold, if applicable.

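### Does the 15 dB threshold-shift rule in section 6.2.4 need a named test, a masking rule and a confirmatory repeat before a shift counts as an adverse event?

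*Protocol*

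**What the plan says.** Section 6.2.4 is a single sentence. A shift from the preoperative baseline "will be reported as an adverse event (AE) when a shift at any frequency exceeds 15 dB HL". The other pieces of the rule stand elsewhere in the protocol:

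- **Measure.** Section 5.1: "Bone conduction thresholds for the study ear will be monitored, to characterize observed unaided thresholds postoperatively". The Study Test Schedule marks the audiograms at visits 4 to 7 "Bone conduction only".
- **Direction.** Section 6.2.2 describes an adverse event as a new untoward occurrence or "the deterioration of a pre-existing medical condition following or during exposure to an investigational product".
- **Baseline.** Section 4.5: "An existing audiogram is acceptable, as long as it has been completed during the last 6 months", provided the required frequencies are present. It also states: "The hearing care professional shall always record the unmasked threshold and record the masked threshold, if applicable".
- **Postoperative masking.** Section 5.1: "Appropriate masking should be used, if needed, according to local practice".
- **Use.** The primary objective in section 3.2 is "To quantify the type and severity of adverse events in the pediatric population implanted with the Osia system". Section 8 sets no hypothesis and plans individual tabulation with descriptive summaries.

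**The concern.** Taken alone, the sentence in section 6.2.4 is loose, and it feeds the primary outcome in at most 20 children, where one child is at least 5% of the sample. Four things look open:

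1. It does not mention bone conduction or the unaided condition. Read literally, it could take in the change from unaided to aided free-field thresholds, which is an intended gain.
2. It does not say the shift must be a worsening.
3. Where section 4.5 yields both an unmasked and a masked preoperative value, it does not say which one is the baseline. A mismatch would be systematic. It would persist on retesting, and it could create a false shift or hide a real one.
4. One reading is enough. With at least 4 frequencies at 4 visits there are 16 or more chances for measurement error to trip the rule. A shift first seen at visit 7 has no later scheduled audiogram.

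If these gaps were real, the count of hearing-related adverse events could be partly an artefact of how thresholds were taken.

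**Working it through.** **Step 1: which threshold, and in which direction.** Section 5.1 and the schedule footnote leave only one kind of postoperative audiogram: unaided bone conduction, study ear. An improvement, or the aided gain the device is meant to give, is neither untoward nor a deterioration, so sections 6.2.1 and 6.2.2 exclude both. Points 1 and 2 come down to a missing cross-reference.

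**Step 2: masking, side by side.**

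| | Preoperative (4.5) | Postoperative (5.1) |
|---|---|---|
| When masking is used | When needed, by local practice | When needed, by local practice |
| Values kept | Unmasked always; masked where it applies | Not specified |
| Site | One (2.2) | Same site |

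The criterion is the same before and after surgery. A mismatch arises only if a child's need for masking changes, or if an accepted outside audiogram was masked differently. Even then the unmasked baseline should be on record whenever section 4.5 was followed.

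**Step 3: random error.** The protocol states no figure to reproduce. Assumptions: normal error with SD s per threshold, recording in 5 dB steps (so exceeding 15 dB means 20 dB or more), 4 frequencies x 4 visits = 16 comparisons against one shared baseline, and no true change. A shift is a difference of two thresholds, so its SD is s x √2.

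Rough check at a difference SD of 7 dB (s about 5): the 5 dB step puts the effective cut at 17.5 dB, so p = 1 − Φ(17.5/7) = 0.0062 per comparison. The chance of at least one in 16, treated as independent, is 1 − (1 − 0.0062)^16 = 9.5%. Simulation with the shared baseline gives 9.4% at that SD. By s:

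| s (dB) | 3 | 4 | 5 | 6 |
|---|---|---|---|---|
| Any false worsening | 0.06% | 1.9% | 9.9% | 23.8% |
| Per 20 children | 0.0 | 0.4 | 2.0 | 4.8 |
| First appearing at visit 7, per 20 | 0.00 | 0.09 | 0.43 | 1.02 |

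At s = 4, 5 and 6, about 92%, 88% and 82% of false flags from visits 4 to 6 are gone at the next scheduled audiogram.

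**Step 4: visit 7.** Section 6.2.7.1.1 requires follow-up until the event resolves or stabilises, makes the investigator responsible for further tests where indicated, and lets the sponsor ask for more measurements. The schedule allows extra visits. A repeat audiogram fits within these provisions.

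**Step 5: a masking mismatch, if one occurs.** Assume 10 dB at one frequency, unmasked before and masked after:

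| s (dB) | 3 | 4 | 5 | 6 |
|---|---|---|---|---|
| Any false worsening, no mismatch | 0.06% | 1.9% | 9.9% | 23.8% |
| Mismatch at one visit | 5% | 11% | 22% | 36% |
| Mismatch at all four visits | 13.2% | 26.4% | 40.1% | 53.2% |

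The bottom row is conditional on a mismatch at every visit. If 10% of children had one (assumed), the excess at s = 4 is (26.4 − 1.9) x 10% = 2.45%, or 0.0245 x 20 = 0.5 of a child. The same sum gives 0.3 at s = 3 and 0.6 at both s = 5 and s = 6.

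In the opposite direction, a real lasting 20 dB loss at s = 4 is flagged in 90.5% with no mismatch and 25.2% with a 10 dB one. At 10% of children affected, that is (90.5 − 25.2) x 10% = 6.5 percentage points of detection.

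**Step 6: what tighter wording would buy.** Every flagged worsening would still be an adverse event, so a confirmation step would only split one descriptive row into two. At s = 4, 5 and 6, a real 20 dB loss first present at visit 7 would be flagged in 67%, 64% and 61% but confirmed in only 52%, 48% and 46%. Many real late losses would sit in the unconfirmed row.

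**The case for a change.** The strongest case for a change is masking. The baseline can be two numbers, no section says which is used, and section 5.1, unlike section 4.5, does not ask for both. If the matching value is not taken at the visit, no later analysis can recover it. The children most exposed would be those with single-sided deafness, whose good ear may respond for the poor one. The repair would cost one sentence and a form field.

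It is true that the pairing is unstated. It does not follow that a mismatch is built in or common. The masking criterion is the same on both occasions and the site is the same, and an audiologist judging a shift can be expected to compare like values. The protocol gives no basis for the size or frequency of a mismatch, and the large percentages need a 10 dB difference repeated at all four visits. The obvious repair also carries a risk: requiring the same masking status at both times could favour an unmasked pair in a child for whom masking is needed.

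On the repeat, the objection is fair that none is automatic. But a sensitive single-reading trigger is a legitimate choice when the purpose is to collect safety information, and the follow-up provisions allow false alarms to be identified.

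**Conclusion.** No change to the plan follows. The test and the direction of the shift are settled by sections 5.1 and 6.2.2 and by the schedule. The masking criterion is the same before and after surgery, and a shift at visit 7 can be rechecked under section 6.2.7.1.1. The unstated choice between unmasked and masked baseline values is a detail the site's audiologists would fill sensibly.

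On assumed error SDs of 3 to 6 dB, chance alone flags between 0 and 4.8 of 20 unchanged children, most of them cleared at the next scheduled audiogram. The masking residue adds roughly 0.3 to 0.6 of a child if one child in ten had a lasting 10 dB mismatch. The error SD, the size of the mismatch and its frequency are all assumptions, since the documents give none of them. The results are listed child by child and summarised descriptively, so no inference depends on the count. A cross-reference from section 6.2.4 to section 5.1 would be tidier, but nothing in the conduct or reading of the trial depends on it.
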